## Introduction:

Leukemia is one of the deadliest diseases having negative impact on people all over the world. Acute Lymphocytic Leukemia (ALL) is a type of WBC cancer, it's a rapidly invasive disease that originates from B- or T-lymphocyte progenitors. Accumulation of lymphoblasts and suppression of normal cells are the main characteristics of the disease course.

Acute lymphoblastic leukemia (ALL) predominantly affects children, with an incidence of 3–4/100,000 in patients under 14 years of age. The five-year survival rate is approximately 90% in children and 65% in adults.

The French–American–British (FAB) categorizes ALL into three subtypes. However, the WHO classification incorporates immunophenotypic and genetic details, offering a more accurate and clinically significant classification, helping to choose therapies and prognostic evaluations according to the distinct characteristics of leukemia. Medical professionals have recently recommended that WHO categorization is better compared to FAB.

Chronic lymphoproliferative diseases (CLPD) are considered as a heterogeneous group of diseases characterized by monoclonal expansion and accumulation of apparently mature lymphocytes, which have a proliferative and/or survival advantage over normal lymphocytes in different organs such as bone marrow, peripheral blood and lymph nodes. This translates into the progressive accumulation of clonal cells and their products, causing peripheral blood and bone marrow lymphocytosis, in addition to lymphadenopathy, splenomegaly or other organomegaly.

Recently, mutations in the genes involved in the spliceosome have attracted considerable interest in different neoplasms. Among the spliceosome mutations, those in the *SF3B1* gene are the most frequent and relevant in haematological diseases. Most human genes encode several mRNA isoforms by the alternative splicing process. Because alternatively spliced mRNA isoforms are often associated with cancer, spliceosome mutations have recently sparked significant interest in different neoplasms.

Splicing of RNA is a fundamental process in eukaryotes. The spliceosome dynamically assembles on messenger RNA precursors (pre-mRNA), removing introns (regions that do not encode proteins) from pre-mRNA, leaving exons (the remainder of RNA transcription) attached.

It is known that *SF3B1* mutations could play multiple roles in the pathogenesis of tumours by dysregulating several cellular functions and pathways, including heme biosynthesis, mitochondrial metabolism, and the NF-κB pathway.

The messenger RNA (mRNA) spliceosome is composed of a complex of five small nuclear ribonucleoproteins (snRNP) U1, U2, U4, U5, and U6 and other proteins and plays critical roles in regulating mRNA splicing and subsequent protein expression. It is assembled through binding of U1 snRNP to the 5' splice site of the pre-mRNA, recruitment of U2snRNP to the 3' splicing site at the intron-exon junction guided by the branch region sequence, and joining of the tri-snRNP U4/U5/U6.

SF3B1, an essential protein in the U2snRNP complex, facilitates U2snRNP binding at the branch point near the 3' splicing site. SF3B1 mutants were shown to alter U2snRNP function by promoting alternative branch-point usage and induction of cryptic 3' splice site selection, thereby generating aberrantly spliced mRNA transcripts subject to nonsense-mediated decay and downregulation of target transcripts and protein expression.

The *SF3B1* gene is located on the long arm of chromosome 2 (2q33.1) and encodes for the biggest subunit (155 KDa) of the splicing factor 3b protein complex. The interaction between the *SF3B1* complex, the 12S unit, and the splicing factor 3a complex gives rise to the U2 small nuclear ribonucleoproteins (snRNP), fundamental for spliceosome assembly and mRNA splicing. The SF3B1 protein is located principally in the nucleus, where it forms nuclear speckles; it is necessary to anchor U2 snRNP to the pre-mRNA by sequence—independently binding the intron branch site.

SF3B1 high proportion in hematopoietic malignancies occurs within codon 700 (K700E) located in the HEAT domain repeat sequence. In addition, hotspots such as R625, K666, and H662 also occur in some proportion , which are thought to have similar mutational functions due to their spatial proximity to K700E in HEAT repeats.

The most common *SF3B1* mutation is an A to G transition that results in lysine to glutamic acid substitution at amino acid position 700 (SF3B1-K700E).

Mutated *SF3B1* gives rise to a protein with a neomorphic activity linked to several mechanisms involved in RNA processing. About half of aberrantly spliced mRNAs are characterized by the presence of premature stop codons, resulting in nonsense-mediated RNA decay and downregulation of the protein expression. Although the wild-type allele is still able to be expressed, the amount of protein produced is unable to compensate for the mutant allele. Another possibility is the translation of new proteins that lack the correct biological function and/or that acquire aberrant functions

A study has shown Hotspot K700E and non-K700E *SF3B1mut* MDS show distinct clinical and mutational profiles in MDS, with K700E showing significantly better Overall survival than non-K700E and *SF3B1wt*. Only the absence of the *SF3B1mut* K700E mutation independently predicted worse Overall survival in MDS. Hence, identification of the *SF3B1* mutation type is important for risk stratification.

In the study by Wang and colleges, somatic mutations of *SF3B1* were found in approximately 15% of patients, making this the second most frequently mutated gene in CLL.

In a cohort of 537 unselected CLL cases, *SF3B1* mutations were present in (8.9%) of cases , The residues surrounding Lys700 were the most frequently mutated (48%).

Quesada and colleges in 2012 studied 279 untreated patients with CLL and found *SF3B1* mutations in 27 (10%) [15]. the most frequent mutation was K700E, occurring in almost half of the cases, No *SF3B1* mutation was detected in 156 patients with non-Hodgkin lymphoma [15]. CLL patients with mutations in *SF3B1* had more aggressive disease and shorter overall survival than patients without these mutations.

Another study provided evidence that the *SF3B1* inhibitor H3B-8800 displays therapeutic effects in mouse models of CLL, particularly when used on CLL cells harbouring *SF3B1* mutations.

To address the functional role of *SF3B1* in T-ALL, *SF3B1* was silenced in T-ALL cell lines using short hairpin RNAs (shRNAs). The cell proliferation rate was significantly decreased upon *SF3B1* silencing, accompanied by an increase in apoptotic cell death and G2-M cell cycle arrest. To further assess the role of *SF3B1* in disease progression *in vivo*, *SF3B1* was silenced in luciferase-expressing CUTLL1 cells and transplanted the cells into immunocompromised mice. *SF3B1* silencing led to a significantly reduced tumour burden and prolonged mouse survival.

## **Subjects and Methods:**

**1- Type of the study:** case control study

**2- Study Setting:** Department of Clinical Pathology in Assiut University Hospital.

**3- Study subjects:**

Study will be conducted on peripheral blood samples of 28 acute lymphoblastic leukemia patients, 28 chronic lymphocytic leukemia patients and 28 control.

**a. Inclusion criteria:**

Patients with acute lymphocytic leukemia or chronic lymphocytic leukemia of both genders at any age.

**b. Exclusion criteria:**

Patients with any other type of malignancies

**c. Sample Size Calculation:**

Based on determining the main outcome variable, the estimated minimum required sample size is 84 patients (28 patient in each group)

The sample was calculated using G\*power software 3.1.9.2., based on the following assumptions:

Main outcome variable is the difference between mean value of Sf3b1 mutation between the groups

1- patients with chronic lymphocytic leukemia

2- patients with acute lymphoblastic leukemia

3- control group free from the disease

Based on clinical experience we expected to find large effect size difference between 3 groups

Main statistical test is one-way Anova to detect the difference between the 3 groups.

Alpha = 0.05

Power = 0.90

Effect size = 0.4

**4 –Study tools (in detail, e.g., lab methods, instruments, steps, chemicals, ...):**

- Medical history (age, sex, complaint of the patients)

- Clinical examination emphasizing on hepatomegaly, splenomegaly and lymphadenopathy.

- Imaging: ultrasound.

- Laboratory investigation: Complete blood count (CBC)

  - Reticulocyte count and Peripheral blood film.

  - Liver and kidney function test

  - Prothrombin time, concentration and INR.

  - Bone marrow examination.

Specific laboratory investigation: ARMS PCR for SF3B1 mutation.

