**Aim(s) of the Research**

1- To evaluate the presence of SF3B1-K700E mutation in acute lymphoblastic leukemia and chronic lymphocytic leukemia using PCR technique

ARMS PCR technique will be used to detect the presence of SF3B1-MUTATION in acute lymphoblastic leukemia and chronic lymphocytic leukemia

2-To determine the effect of presence of SF3B1-K700E mutation with other laboratory findings.

determine if the presence of SF3B1-mutation can affect the clinical data as severity of disease or organomegaly and laboratory data as count of white blood cells and platelet and hemoglobin level using automated cbc analyser and bone marrow of the patients (cellularity and count of blast cells) and result of flow cytometry

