#### **-Data management and analysis:**

Analysis of data by SPSS program. Data will be expressed as mean $\pm$  SD, number and percentage. Correlation between categorical variables will be performed in 2x2 contingency tables using Fisher's exact test. Comparison between metric variables will be done using Mann-Whitney test and Wilcoxon signed ranks test. Exact p value (2-sided) will be calculated and a value  $\leq 0.05$  is considered statistically significant.

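### Both aims target SF3B1-K700E, but the main outcome and the assay line say only SF3B1 mutation, a wider class; separately, the outcome is binary and the ANOVA-based 90% power does not apply to it

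*Protocol*

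**What the plan says.** **Target.** In the Protocol's Aim(s) of the Research, aim 1 reads "To evaluate the presence of SF3B1-K700E mutation in acute lymphoblastic leukemia and chronic lymphocytic leukemia using PCR technique" and aim 2 reads "To determine the effect of presence of SF3B1-K700E mutation with other laboratory findings". The explanatory line under aim 1 drops the allele: "ARMS PCR technique will be used to detect the presence of SF3B1-MUTATION in acute lymphoblastic leukemia and chronic lymphocytic leukemia". The line under aim 2 drops it too.

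Under Sample Size Calculation the main outcome is "Main outcome variable is the difference between mean value of Sf3b1 mutation between the groups", and under Study tools the assay is given as "ARMS PCR for SF3B1 mutation". The expected-benefit sentence in section 3.1 also speaks of SF3B1 mutation in general. No section shown gives a codon, allele or primer for the ARMS PCR.

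**Background.** The Introduction treats the two terms as different. It lists R625, K666 and H662 as further hotspots. For CLL it cites SF3B1 mutation rates of 8.9%, 10% (27 of 279) and about 15%. In the 279-patient series it puts K700E at nearly half of the mutated cases. It gives no SF3B1 rate for ALL.

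**Analysis.** The sample size section says "Main statistical test is one-way Anova to detect the difference between the 3 groups" and "Effect size = 0.4", with alpha 0.05 and power 0.90, giving 28 per group. The Data management and analysis section says "Correlation between categorical variables will be performed in 2x2 contingency tables using Fisher's exact test".

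**The concern.** There are two separate issues.

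**The target of the outcome.** The aims ask about one allele, while the main outcome names the whole gene. On the Protocol's own background figures, K700E covers only about half of SF3B1-mutated CLL. If a K700E-only result is reported under the outcome as worded, the SF3B1 mutation rate in CLL is understated by about half, and a negative result may be taken to say more than the assay can show. Most patients will be negative, so the meaning of a negative matters.

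**The scale of the outcome.** Presence of a mutation is yes or no, whichever allele is meant. A mean value compared by ANOVA at f = 0.4 is not the analysis that the data section plans for categorical variables. The effect size is also not tied to any mutation rate in the Protocol. At stake is whether the stated 90% power describes this study.

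**Working it through.** **1. The stated sample size.** One-way ANOVA with 3 equal groups, f = 0.4, alpha 0.05; noncentral F with lambda = N × f² and df 2 and N − 3. Power is 0.895 at N = 81 and 0.907 at N = 84. The stated 84 (28 per group) reproduces as an ANOVA calculation.

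**2. Inputs for CLL.** Any-SF3B1 rate s = 0.089 to 0.15 (Introduction). K700E share = 0.45 to 0.50, which is an assumed reading of nearly half. The Introduction's 48% refers to residues around Lys700, not K700E alone, so it is not used as the K700E share. Group size is 28. A K700E-only assay and one variant per patient are assumed.

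**3. Expected counts among 28 CLL patients.**
- Any SF3B1: 28 × 0.089 = 2.5; 28 × 0.15 = 4.2.
- K700E rate p = s × share: 0.089 × 0.45 = 0.040; 0.15 × 0.50 = 0.075. Counts: 1.1 to 2.1.
- Other variants among the negatives, 28 × (s − p): 28 × 0.089 × 0.50 = 1.2; 28 × 0.15 × 0.55 = 2.3.
- As a share of K700E-negative patients, (s − p)/(1 − p): 4.7% to 8.8%.
- Chance of at least one such patient, 1 − (1 − (s − p))^28: 72% to 91%.
- Chance of no K700E carrier, (1 − p)^28: 32% at p = 0.040, 11% at p = 0.075.

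Sensitivity: if nearly half means 13 of 27, its exact 95% interval is 29% to 68%. The chance of at least one other-variant carrier then runs from 56% to 96%.

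**4. Effect size implied by the CLL rates.** For group proportions, f = SD of the three proportions / √(mean of p(1 − p)). Controls are assumed 0, and ALL is assumed either 0 or equal to CLL. Power is the ANOVA power at N = 84.

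| Rate in CLL | ALL | f | Power |
|---|---|---|---|
| K700E 4.0% | = CLL | 0.0189/0.160 = 0.12 | 14% |
| K700E 4.0% | 0 | 0.0189/0.113 = 0.17 | 25% |
| K700E 7.5% | = CLL | 0.0354/0.215 = 0.16 | 24% |
| K700E 7.5% | 0 | 0.0354/0.152 = 0.23 | 45% |
| Any 8.9% | = CLL | 0.0420/0.232 = 0.18 | 29% |
| Any 8.9% | 0 | 0.0420/0.164 = 0.26 | 53% |
| Any 15% | = CLL | 0.0707/0.292 = 0.24 | 48% |
| Any 15% | 0 | 0.0707/0.206 = 0.34 | 80% |

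Reaching f = 0.4 would need a CLL rate of about 19% (ALL 0) or 32% (ALL equal to CLL). Both exceed the highest any-SF3B1 rate cited.

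**5. Fisher's exact test, CLL against controls, 28 each.** 5 v 0 gives p = 0.051 and 6 v 0 gives p = 0.023, so with no positive controls at least 6 positives are needed. The chance of 6 or more is 0.1% to 1.6% for K700E (4.0% to 7.5%) and 3.4% to 23.5% for any SF3B1 (8.9% to 15%).

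**The case against.** **The short form may be plain shorthand.** The ARMS line follows directly on aim 1 and expands its PCR technique, so the natural reading is an assay for the K700E mutation just named. No other allele is named as a study target. This largely stands, and it is why the numbers above assume a K700E-only assay. It does not rescue the main outcome, which sits in another section and names a class that the Introduction shows to be about twice as large in CLL.

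**A reader might infer that negatives will be counted as having no SF3B1 mutation.** The Protocol has no such rule. It gives no coding or label for a negative result, and such detail is commonly left to an analysis plan. The wording permits that misreading but does not prescribe it.

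**A reader might infer that aim 2 is contaminated by carriers of other variants.** Aim 2 as numbered asks about K700E, and for that question such carriers belong in the K700E-negative group. Only the label is at issue. The numbers are also small: 1 to 2 of 28, in a CLL comparison that would have only 1 or 2 positives.

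**A reader might infer that the power problem comes from the allele wording.** It does not. The any-SF3B1 rates also give f below 0.4, and the outcome is binary either way. The power point stands on its own.

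**Conclusion.** The concern holds in limited form. The main outcome and assay line name a wider class than the aims. If the assay is K700E-only, the outcome label covers about twice as many CLL patients as the assay can find (2.5 to 4.2 against 1.1 to 2.1 of 28). The K700E rate and the K700E comparison in aim 2 are unaffected; what changes is the label and the reading of a negative. For ALL the effect cannot be sized, because the Protocol gives no rate.

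Independently, the 90% power rests on an outcome scale and an effect size that do not fit mutation presence. On the Protocol's CLL rates, ANOVA power at N = 84 would be roughly 14% to 45% for K700E and 29% to 80% for any SF3B1.

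These figures depend on the assumed 45% to 50% K700E share being applied to cohorts for which no share is given, on controls at 0, and on ALL at 0 or equal to CLL. ANOVA power for rare binary data is itself only an approximation, so the ranges show the order of the shortfall and are not replacement values.

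**What to change.** 1. Under Study tools, name the ARMS target. Under Sample Size Calculation, define the main outcome as SF3B1-K700E detected or not detected.
2. Use the same term in the lines under both aims and in section 3.1, and label the aim 2 groups K700E-positive and K700E-negative.
3. Report a negative as K700E not detected, other SF3B1 variants not assessed.
4. If the assay covers further hotspots, list them and widen the aims instead.
5. Under either choice, replace the mean, ANOVA and f = 0.4 basis with a comparison of proportions consistent with the planned Fisher's exact test. State the assumed rate in each group, and whether the main comparison is across all three groups or pairwise. Give the power at 28 per group in place of 90%.

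Cost: revised wording in three sections and one new power calculation. The study claims less (K700E, not SF3B1 as a whole) and states a less favourable power. Assay and enrolment need not change.

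### The 0.90 power for 84 subjects comes from an ANOVA of a mean, but the endpoint is K700E present or absent; at the K700E rates implied by the protocol's introduction, an exact three-group test has about 2% to 15% power (controls at 0, ALL at 0 to 3.6%)

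*Protocol*

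**What the plan says.** The Sample Size Calculation section of the protocol defines the outcome as a mean: "Main outcome variable is the difference between mean value of Sf3b1 mutation between the groups". It then says: "Main statistical test is one-way Anova to detect the difference between the 3 groups". The inputs are alpha 0.05, power 0.90 and effect size 0.4, giving 84 subjects, 28 each with CLL, ALL and no disease. The effect size has one justification: "Based on clinical experience we expected to find large effect size difference between 3 groups".

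The Aims section describes a different quantity: "To evaluate the presence of SF3B1-K700E mutation in acute lymphoblastic leukemia and chronic lymphocytic leukemia using PCR technique". The assay is ARMS PCR, used to detect whether the mutation is there.

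The Data management and analysis section does not mention ANOVA. For categorical data it says "Correlation between categorical variables will be performed in 2x2 contingency tables using" Fisher's exact test. For metric data it names Mann-Whitney and Wilcoxon signed ranks tests. P values are exact and two-sided.

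The Introduction gives SF3B1 mutation rates in CLL from three studies. In one, mutations "were found in approximately 15% of patients". In a cohort of 537 the rate was 8.9%, with 48% of the mutations around codon 700. In 279 untreated patients it was 10%, and "the most frequent mutation was K700E, occurring in almost half of the cases". No rate is given for ALL or for controls.

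**The concern.** A yes/no result per subject has no mean in the sense of the power calculation, and the protocol describes no quantitative measure, such as allele burden or expression, that would have one. The test named as the main one does not fit the endpoint and is missing from the analysis section. The effect size is not tied to any carrier rate.

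Two things are at stake. First, the protocol promises 90% power for its main comparison. If the true figure is far lower, a non-significant result is the expected one and could be misread as evidence that the groups do not differ. Second, the two sections together leave the main test open, and some data sets would be significant under one candidate test and not under another.

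**Working it through.** **1. The stated figure.** One-way ANOVA, 3 groups, f = 0.4, N = 84, alpha 0.05, noncentral F with noncentrality f² × N = 0.16 × 84 = 13.44: power 0.907. At N = 81 it is 0.895. So 84 is the smallest balanced N that reaches 0.90, and the arithmetic is right for its inputs.

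**2. K700E rates in CLL from the Introduction.**
- Cohort of 537: 8.9% × 48% = 4.3%. This takes the share around codon 700 as K700E.
- 279 untreated patients: about half of 10% = 5%.
- The 15% study: half of 15% = 7.5%. No K700E share is given for this study; one half is borrowed from the others.

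**3. Assumptions.** Controls 0; ALL between 0 and 3.6% (1 in 28).

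**4. What f = 0.4 means for a proportion.** f is the SD of the group means divided by the square root of the average of p(1 − p). For carrier rates (p, 0, 0) this becomes f = √[2p / (3(1 − p))]. Setting f = 0.4 gives 0.48(1 − p) = 2p, so p = 0.48/2.48 = 19.4%. With ALL at 3.6%, the CLL rate needed is about 24.5%. In the other direction, with ALL at 0, f is 0.17 at 4.3%, 0.19 at 5%, 0.23 at 7.5% and 0.34 at 15%.

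**5. Rejection thresholds at 28 per group, carriers in CLL only.**

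| CLL carriers | ANOVA on 0/1 data | Exact 3x2 (Fisher-Freeman-Halton) | Fisher, CLL vs control |
|---|---|---|---|
| 2 | 0.13 | 0.33 | 0.49 |
| 3 | 0.044 | 0.103 | 0.24 |
| 4 | 0.014 | 0.032 | 0.11 |
| 5 | 0.004 | 0.010 | 0.0515 |
| 6 | 0.001 | 0.003 | 0.023 |

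With carriers in CLL only, the ANOVA rejects from 3 carriers, the exact 3x2 test from 4 and the pairwise Fisher test from 6.

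**6. Power.** Binomial probabilities are summed over all CLL and ALL counts whose p value is at most 0.05, with controls at 0.

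| CLL rate | Exact 3x2, ALL 0 | Exact 3x2, ALL 3.6% | ANOVA on 0/1, ALL 0 | Fisher, CLL vs control |
|---|---|---|---|---|
| 4.3% | 3% | 2% | 12% | 0.1% |
| 5% | 5% | 3% | 16% | 0.2% |
| 7.5% | 15% | 8% | 35% | 1.6% |
| 15% (any SF3B1 mutation) | 62% | 44% | 81% | 24% |

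**7. How often the test matters.** With 0 to 2 CLL carriers and none elsewhere, all three tests are non-significant. With ALL at 0, that is 88% of samples at a CLL rate of 4.3% and 65% at 7.5%. At those two rates the ANOVA and the exact 3x2 test disagree in 9% and 20% of samples with ALL at 0, and in 5% and 8% with ALL at 3.6%.

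**The case against.** The arithmetic is not in dispute; the objections concern how firm the range is and how much it matters.

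- **The rates are partly inferred.** Only the 5% follows closely from the text. The 48% refers to residues around codon 700, and the half share applied to the 15% study is borrowed. This stands as a caution. Without the borrowed figure, the upper end of the power range falls from 15% to 5%.
- **The range of ALL rates is not sourced.** This stands too: 2% to 15% is no bound over all possible ALL rates. With CLL at 5% and controls at 0, exact 3x2 power is 15%, 39% and 65% at ALL rates of 10%, 15% and 20%. None of these reaches 0.90.
- **The wording alternates between K700E and SF3B1 mutation.** For any SF3B1 mutation, with ALL and controls at 0, exact power is 24% at 8.9%, 31% at 10% and 62% at 15%. Both aims name K700E, so that reading is the better one, and the 0.90 fails under either.
- **A separate SAP could add a three-group test.** It could, but the protocol itself names ANOVA of a mean as the main test and elsewhere plans proportion-based tests. That conflict is between two stated sections.
- **The study is non-interventional and its first aim is largely descriptive.** That lowers the consequences, but does not make the stated power correct.

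**Conclusion.** The concern holds. The claimed 0.90 belongs to an analysis of means that the study cannot carry out on a present/absent result, and the effect size of 0.4 exceeds what any CLL rate in the Introduction implies under the stated assumptions. At the implied K700E rates of 4.3% to 7.5%, with controls at 0 and ALL at 0 to 3.6%, the exact three-group test has about 2% to 15% power. Applying the ANOVA to 0/1 data does not rescue the claim: 12% to 35% with ALL at 0. Taking the highest quoted rate, 15% for any mutation, the best case is 62% for the exact test and 81% for the ANOVA. The choice of test changes the conclusion only in a minority of samples; the main fault is the power claim and the contradictory definition of the main analysis. Both need correcting before the data are analysed.

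**What to change.** - **Sample size section, outcome:** replace the mean with the proportion K700E-positive in each group.
- **Sample size and analysis sections, test:** name one main test suited to a proportion, such as the Fisher-Freeman-Halton exact test on the 3x2 table (group by K700E status) at two-sided 0.05. Run the pairwise 2x2 Fisher tests at 0.05 only if it is significant; with three groups this sequence controls the familywise error. An exact permutation chi-square test would serve equally well: its power was the same in the scenarios checked with ALL and controls at 0.
- **Power statement:** replace effect size 0.4 and power 0.90 with the power of that test at 28 per group over a stated range of CLL and ALL rates, as in the table above. Keep 84 and call the group comparison exploratory.
- **Aim 1:** report each group's proportion with an exact (Clopper-Pearson) 95% interval. For scale, 0 of 28 gives 0 to 12.3% and 2 of 28 gives 0.9% to 23.5%.
- **Aim 2:** keep 2x2 Fisher and Mann-Whitney tests for carriers against non-carriers.

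The cost is rewording two sections, with no added subjects; SPSS, the planned software, runs exact tests on larger tables. The price is a much lower stated power and pairwise tests that will usually go uninterpreted: at the K700E rates above, the global test is non-significant in about 85% to 98% of samples. If the sponsor prefers a confirmatory comparison, the exact test needs about 155 per group at a CLL rate of 4.3% or 88 at 7.5% for 90% power, with ALL and controls at 0.
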